3.2 Adherence

3.2.1 Adherence to Allocated Treatment

CPAP therapy will be monitored remotely using AirView™ (ResMed) and in addition data will be downloaded from the device SD card every three months. The data will be downloaded in the ResScan software program for compliance calculations.

Adherence to the intervention will be presented as mean (\pm SD) duration of adherence to CPAP therapy in the last three months of treatment before ablation procedure (period of primary endpoint). The residual apnea-hypopnea index during CPAP use, as measured by the CPAP device will also be presented as average events per hour.

The number and % of participants using the CPAP device more than four hours per night will be presented.

3.3 Analysis Populations

The Enrolled set will include all patients who have provided informed consent and have been included into the study data base.

The Full Analysis Set (FAS) will be defined as all patients randomly assigned to a treatment group.

The Per Protocol Set (PPS) will include all randomised patients who have at least one assessment of the efficacy variable burden of atrial fibrillation, are on their randomized treatment CPAP or usual care. In the CPAP group, patients with no duration of the CPAP device the last three months will be excluded for the PPS.

4 Trial Population

4.1 Screening Data, Eligibility and Recruitment

The total number of screened patients and reasons for not entering the trial will be summarised and tabulated.

A CONSORT flow diagram (appendix A) will be used to summarise the number of patients who were:

- assessed for eligibility at screening
- eligible at screening
- ineligible at screening*
- eligible and randomised
- eligible but not randomised*

STATISTICAL ANALYSIS PLAN for Effect of treatment of sleep apnea in patients with paroxysmal atrial fibrillation.

- received the randomised allocation
- did not receive the randomised allocation*
- lost to follow-up*
- discontinued the intervention*
- randomised and included in the primary analysis
- randomised and excluded from the primary analysis*

*reasons will be provided.

4.2 Withdrawal/Follow-up

The number of withdrawals will be presented.

A withdrawal is defined as participants who withdrew consent, and for which data collected cannot be used.

A lost to follow up is defined as participants who withdrew from follow-up, but allowed data collected to be used.

The status of eligible and randomised patients at trial end will be tabulated by treatment group according to

- completed intervention and assessments
- completed assessments but not intervention
- withdrew consent
- lost to follow-up

4.3 Baseline Patient Characteristics

The following patient demographics and baseline characteristics will be summarised:

Age, years

Gender, no. (%)

BMI, kg/m²

Neck circumference, cm

Waist-to-hip ratio

LVEF, %

AHI, per hour

Obstructive apnea index, per hour

Central apnea index, per hour

Minimum SpO₂, %

SpO₂ time < 90%, %

Epworth Sleepiness score

FOSQ score

STATISTICAL ANALYSIS PLAN for Effect of treatment of sleep apnea in patients with paroxysmal atrial fibrillation.

SF-36 (Physical and Mental Component Summary)

Cardiovascular disease, no. (%)

Hypertension no. (%)

Diabetes mellitus no. (%)

Stroke/TIA no. (%)

COPD/asthma no. (%)

Previous DC cardioversion no. (%)

Beta-blocker no. (%)

ACE-I + ARB no. (%)

Calcium channel blocker no. (%)

Diuretic no. (%)

Statin no. (%)

NOACs no. (%)

Antidiabetic medication no. (%)

Flecainide no. (%)

Dronedarone no. (%)

Hb, g/dl

Creatinine, mcmol/l

NT-proBNP, ng/L

Troponin T, ng/L

Patient demographics and baseline characteristics will be summarised by randomised treatment arm and overall using descriptive statistics (N, mean, standard deviation, median, 25/75 percentiles for continuous variables, and number and percentages of patients for categorical variables. There will be no statistical analysis of treatment difference. Any clinically important imbalance between the treatment groups will be noted.

5 Analysis

5.1 Outcome Definitions

5.1.1 Primary Outcome

Difference between CPAP treatment and usual care in change in AF burden (% of time in AF, as measured by loop recorder) from baseline (one month prior to randomization) to the *last three months of the intervention period*.

5.1.2 Secondary Outcomes

STATISTICAL ANALYSIS PLAN for Effect of treatment of sleep apnea in patients with paroxysmal atrial fibrillation.

- Difference between CPAP treatment and usual care in change in AF burden (% of time in AF, as measured by loop recorder) from baseline (one month prior to randomization) to the *last month of the intervention period*.
- Difference between CPAP treatment and usual care in change in AF burden (% of time in AF, as measured by loop recorder) from baseline (one month prior to randomization) to the *last five months of the intervention period*.
- Difference between CPAP treatment and usual care in the proportion of patients with at least 25% reduction of AF burden (% of time in AF, as measured by loop recorder) from baseline (one month prior to randomization) to the *last three months of the intervention period*.
- Difference between CPAP treatment and usual care in change in AF symptom burden (assessed with the Atrial Fibrillation Severity Scale [AFSS] questionnaire) from baseline to five months after randomization:
 - AFSS Domain: frequency
 - AFSS Domain: duration
 - AFSS Domain: severity
 - AFSS AF burden
 - AFSS symptom score
 - AFSS Global well-being
- Difference between CPAP treatment and usual care in change in Quality of life (assessed with the Short Form-35 [SF-36] questionnaire) from baseline to five months after randomization:
 - SF-36 Component Summary: Physical
 - SF-36 Component Summary: Mental
- Difference between CPAP treatment and usual care in change in sleep quality and symptoms of OSA from baseline to five months after randomization:
 - Epworth Sleepiness Scale (ESS) sum score
 - Functional Outcomes of Sleep Questionnaire (FOSQ) sum score
 - Berlin Questionnaire sum score
 - Berlin Questionnaire sum score ≥ 2 (dichotomous)
 - Stop-Bang Questionnaire sum score
 - Stop-Bang Questionnaire sum score ≥ 3 (dichotomous)

5.1.3 Exploratory Outcomes

Difference between CPAP treatment and usual care in:

- Changes in cardiac structure and function (on echocardiography)
- Changes in cardiac biomarkers (troponin T and NT-proBNP)

STATISTICAL ANALYSIS PLAN for Effect of treatment of sleep apnea in patients with paroxysmal atrial fibrillation.

- Changes in inflammatory and anti-inflammatory biomarkers in plasma and serum:
 - CRP, TNF- α , TNFRII, interleukin-6, interleukin-10, chemokines (MCP-1), endothelial function (von Willebrand), and metalloproteinases
- Changes in gene expression of white blood cells, and relationship with AF burden
- Activity patterns around the onset of PAF (assessed using Garmin Vivofit and activity recording)
- Change in body composition (on bioelectric impedance analysis)
- Lung function (spirometry)

5.1.4 Summary of Outcomes

Level	Outcome	Timeframe	Type
Primary	1. Change in AF burden	Baseline to last three months	Continuous
Secondary	2. Change in AF burden	Baseline to last month	Continuous
	3. Change in AF burden	Baseline to last five months	Continuous
	4. Proportion with more than 25% reduction in AF burden	Baseline to last three months	Dichotomous
	5. Change in AF symptoms (AFSS frequency)	Baseline to five months	Continuous
	6. Change in AF symptoms (AFSS duration)	Baseline to five months	Continuous
	7. Change in AF symptoms (AFSS severity)	Baseline to five months	Continuous
	8. Change in AF symptoms (AFSS AF burden)	Baseline to five months	Continuous
	9. Change in AF symptoms (AFSS AF symptom score)	Baseline to five months	Continuous
	10. Change in AF symptoms (AFSS AF global well-being)	Baseline to five months	Continuous

STATISTICAL ANALYSIS PLAN for Effect of treatment of sleep apnea in patients with paroxysmal atrial fibrillation.

11. Change in quality of life (SF-36 physical component)	Baseline to five months	Continuous
12. Change in quality of life (SF-36 mental component)	Baseline to five months	Continuous
13. Change in sleep quality (ESS sum score)	Baseline to five months	Continuous
14. Change in sleep quality (FOSQ sum score)	Baseline to five months	Continuous
15. Change in symptoms of OSA (Berlin sum score)	Baseline to five months	Continuous
16. Symptoms of OSA (Berlin sum score ≥ 2)	Five months	Dichotomous
17. Change in symptoms of OSA (Stop-Bang sum score)	Baseline to five months	Continuous
18. Symptoms of OSA (Stop-Bang sum score ≥ 3)	Five months	Dichotomous

5.2 General Definitions and Derived Variables

5.2.1 Duration of atrial fibrillation

Duration of atrial fibrillation measured in hours and minutes will be converted to % of time in atrial fibrillation.

5.2.2 Body Mass Index

Body Mass Index (BMI) = Body weight in kilograms divided by the square of the height in meters.

5.2.3 Waist-hip ratio

Waist-hip ratio = The measured circumference of the waist divided by the measured circumference of the hip.

5.3 Analysis Methods

5.3.1 Primary Outcome

The primary outcome, difference between CPAP and usual care in change in AF burden from baseline to the last three months of the intervention period will be analysed with linear regression, with AF burden last three months as the dependent variable and treatment (CPAP vs usual care), study site (St Olavs University Hospital, Trondheim vs Rikshospitalet,

STATISTICAL ANALYSIS PLAN for Effect of treatment of sleep apnea in patients with paroxysmal atrial fibrillation.

Oslo), and AF burden at baseline as explanatory variables. The mean difference between the two treatment groups with a 95% confidence interval will be reported, together with a P-value for the null hypothesis of no treatment difference.

The primary analysis will be done on the Full Analysis Set. A secondary analysis will be done on the Per Protocol Set.

5.3.2 Secondary Continuous Outcomes

All secondary continuous outcomes (see table in Section 5.1.4) will be analysed in the same manner as the primary outcome, with linear regression with the last measurement as the dependent variable and treatment, study site, and baseline measurement as explanatory variables. The results will be reported as the mean treatment difference with a 95% confidence interval, and P-value for the null hypothesis of no treatment difference.

All secondary continuous outcomes will be analysed on the Full Analysis Set.

5.3.3 Secondary Dichotomous Outcomes

The dichotomous outcomes will be analysed with Newcombe hybrid score 95% confidence intervals² for the difference between proportions and P-values for the Fisher mid-P test² of the null hypothesis of equal proportions.

The secondary dichotomous outcomes will be analysed on the Full Analysis Set.

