4.3 Intervention

All participants will receive standardized education in habits that promote improved sleep quality and reduced cardiovascular risk including advice on diet and exercise

After baseline evaluation, a stratified permuted block design with stratification according to site will be used, and the patients randomized to one of two interventions: Active treatment for SA or just sleep education (controls).

Active treatment: Patients will be treated with automatic CPAP (Continuous positive airway pressure) (ResMed) which automatically adjusts pressure levels based on a patient's breathing. The automatic CPAP is effective in treating obstructive sleep apnea by preventing the soft tissues of the upper airway from narrowing or collapsing. If the patients have central apneas in addition (average cAI >10 during mask test week) they will be treated with an ASV (adaptive servo-ventilation) (ResMed). The ASV device contains an algorithm which treats both obstructive and central sleep apnea. The patients will be followed by phone, rapid access to the clinic, and regular follow up (see flow chart). Patients with problems or non-compliant patients will be invited to the clinic for additional education and troubleshooting. Compliance is defined as > 4 hours per night.

Controls: No interventions besides education in healthy lifestyle and sleep education will be given

All patients will be followed closely by regular visits to the outpatient clinic or by phone. In addition they will be followed by telemonitoring to assess the patient's treatment and compliance to the device.

Definition of outcome**Phase 1:***Primary outcome*

- Reduction in total burden of AF (Reveal device date)

Secondary outcome after treatment of SA in AF study

- Reduction in recurrence rate of AF after ablation
- Reduction in AF symptom burden as assessed by Atrial Fibrillation Severity Scale (AFSS)
- Change in quality of life (QoL) as assessed by SF 36
- Change in sleep quality and symptoms of obstructive sleep apnea as measured using the Epworth Sleepiness Scale (ESS) score, the Functional Outcomes of Sleep Questionnaire (FOSQ) and the Berlin Questionnaire and Stop-Bang Questionnaire.
- Change in blood levels of catecholamine's, NT-proBNP, troponins and inflammatory and vasoactive substances
- Concordance in sleep date recorded from the PG and the Reveal device data

Echocardiography

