5.3.5 Missing Data

Missing data will be imputed such that the patient with missing data will have no change from baseline on the missing outcome. This can be considered a worst-case imputation strategy for the CPAP treatment.

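### Outcomes 16 (Berlin ≥ 2) and 18 (Stop-Bang ≥ 3) are compared as unadjusted five-month proportions, and their baseline status is not tabulated: the test is valid, but site and baseline adjustment is a cheap improvement

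*SAP*

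**What the plan says.** SAP 5.3.3 gives one method for the three dichotomous outcomes (4, 16 and 18): "The dichotomous outcomes will be analysed with Newcombe hybrid score 95% confidence intervals" for the difference in proportions, with a Fisher mid-P test. It adds: "The secondary dichotomous outcomes will be analysed on the Full Analysis Set". No site or baseline term is named, and SAP 5.3.6 and 5.3.7 add no adjusted analysis of these outcomes.

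Other parts of the documents that bear on this:

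- **Continuous outcomes.** SAP 5.3.2 specifies "linear regression with the last measurement as the dependent variable and treatment, study site, and baseline measurement as explanatory variables". This covers the Berlin and Stop-Bang sum scores (outcomes 15 and 17). SAP 5.3.1 uses the same structure for the primary outcome.
- **Randomisation.** Protocol 4.3 states that "a stratified permuted block design with stratification according to site will be used". SAP 2.2 gives block sizes but does not mention the stratification.
- **Baseline table.** SAP 4.3 opens with "The following patient demographics and baseline characteristics will be summarised" and lists ESS, FOSQ and SF-36, but neither Berlin nor Stop-Bang. It ends with "Any clinically important imbalance between the treatment groups will be noted".
- **Missing data.** SAP 5.3.5: "Missing data will be imputed such that the patient with missing data will have no change from baseline on the missing outcome".
- **Outcome definition.** SAP 5.1.2 lists both outcomes under "Difference between CPAP treatment and usual care in change in sleep quality and symptoms of OSA from baseline to five months after randomization". SAP 5.1.4 gives their timeframe as five months only.
- **Status.** SAP 2.4.1 classes everything except the primary analysis as supportive or exploratory.

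**The concern.** The same questionnaire is handled in two ways. As a sum score it is adjusted for site and for its own baseline; cut at a threshold it is adjusted for neither, and the SAP gives no reason. Repeated answers from the same patient are likely to be correlated, so baseline status should explain some of the five-month variation. Leaving it out forgoes that precision. It also lets a chance difference between the arms at baseline carry into the five-month difference.

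Two features add to this. The SAP promises to note important imbalances, but its table would not show one in these two instruments. And when a five-month value is missing, 5.3.5 substitutes baseline status, so part of any imbalance enters the outcome directly.

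**Working it through.** **Inputs from the documents.** 50 patients per arm, 1:1 (SAP 2.1); two sites; two-sided 5% level (SAP 2.3). The plan gives no figure for outcomes 16 or 18. Its own sample size, for the primary endpoint, does reproduce. The difference is 0.25 × 34 = 8.5 points. With n = 2(1.96 + 0.84)² SD² / 8.5², SD 12 gives 32 per arm (33 with the t distribution) and SD 15 gives 49 (50 with t). This does not bear on the present point.

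**Assumptions.** The documents give no prevalence of positive status and no correlation (phi) between baseline and five-month status. Phi 0.2, 0.3 and 0.5 are used below, with baseline positivity of 60% or 90%.

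**Step 1: how often the arms differ at baseline.** The SD of the chance difference is √(2p(1−p)/50).

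- p = 0.6: √(2 × 0.6 × 0.4/50) = 0.098.
- p = 0.9: √(2 × 0.9 × 0.1/50) = 0.060.

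A gap of 10 points or more means at least 5 patients out of 50. With a continuity correction the threshold is 4.5/50 = 0.09. That gives z = 0.09/0.098 = 0.92, or about 36% of trials, and z = 0.09/0.060 = 1.5, or about 13%. Simulation agrees.

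**Step 2: precision and power.** As a guide, adjustment multiplies the standard error by about √(1 − phi²): 0.980, 0.954 and 0.866. The simulated reductions are slightly smaller because the extra terms must be estimated. The unadjusted SE for 60% versus 35% is √(0.6 × 0.4/50 + 0.35 × 0.65/50) = 0.097. Then 0.25/0.097 − 1.96 ≈ 0.62, which is power of about 73%.

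Simulated results (60% positive at baseline; 60% versus 35% at five months; linear model with HC2 standard errors):

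| Phi | Fall in SE | Power, unadjusted mid-P | Power, adjusted | Mean CI width, Newcombe | Mean CI width, adjusted |
|---|---|---|---|---|---|
| 0.2 | 1.5% | 74% | 73% | 0.363 | 0.378 |
| 0.3 | 4.2% | 73% | 75% | 0.363 | 0.368 |
| 0.5 | 13% | 72% | 83% | 0.363 | 0.334 |

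At phi 0.2 the adjusted interval is 0.378/0.363 = 1.04 times as wide as Newcombe's. With 90% positive at baseline and 80% versus 55% at five months, the SE falls 1.5% and 4.0% at phi 0.2 and 0.3. Power is 76/76% unadjusted and 79/81% adjusted, partly because mid-P is conservative there (null rejection 4.2–4.3%). Phi 0.5 is not attainable in that CPAP arm: the maximum is √(0.55 × 0.1/(0.9 × 0.45)) = 0.37.

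**Step 3: false positives when the arms differ by 10 points or more at baseline.** The two-sided mid-P can halve the weight of every table as probable as the observed one (A), or of the observed table only (B). The SAP refers to a textbook for the definition, so both are shown. Ranges cover repeated simulation runs.

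| Setting under no effect | Phi | Variant A | Variant B |
|---|---|---|---|
| 60% baseline, 60% at five months | 0.2 | 5.6–6.1% | 3.6% |
| | 0.3 | 6.0–6.7% | 3.8–4.6% |
| | 0.5 | 9.0–9.3% | 6.1–6.5% |
| 90% baseline, 80% at five months | 0.2 | 5.5–5.7% | 4.1% |
| | 0.3 | 6.8–7.1% | 6.1% |
| | 0.5 | 11.1–11.9% | 9.1% |

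The adjusted analysis stays at about 5% (4.8–5.8% across runs). An excess under both variants appears only at phi 0.5 with 60% positivity, and from about phi 0.3 with 90%. Over all trials the unadjusted test does not exceed 5%: at 60% positivity, variant A gives 4.9/4.4/2.8% in the remaining, better balanced trials and about 5% overall.

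**The case against.** The strongest reply is that nothing here is an error. Section 5.3.3 is complete and can be carried out as written. Under randomisation the unadjusted comparison is valid and unbiased, the outcomes are supportive, and the matching sum scores are already adjusted. All of that stands.

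The benefit is also unknown. At phi 0.2 and 60% positivity there is no power gain and the interval is wider. At very high positivity the baseline term often has to be dropped. That stands too. If the SAP means variant B, the conditional excess at 60% positivity disappears at phi 0.2 and 0.3. Variant B has lower power, however (66–67% in the setting of the first table), which favours adjustment.

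A reader might infer stronger claims that the documents do not support:

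- **The planned test is biased or inflates type I error.** It does neither; the excess exists only conditional on a baseline imbalance and is offset in balanced trials.
- **Every continuous outcome is adjusted.** Sections 5.3.1 and 5.3.2 cover the primary and secondary ones; no method is stated for the exploratory outcomes.
- **Only these two instruments are missing from the baseline table.** AFSS and baseline AF burden are not listed either.
- **The 5.1.2 and 5.1.4 wordings make the analysis ambiguous.** Sections 5.1.4 and 5.3.3 agree on five-month proportions, so 5.1.2 needs only an editorial correction.

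Outcome 4 is different: baseline is part of its definition, so it needs no baseline term.

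**Conclusion.** The point holds as a minor, inexpensive improvement. Outcomes 16 and 18 are compared without the stratification factor and without a baseline value that is already collected, unlike the primary and all secondary continuous outcomes, and their baseline status would not be tabulated.

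The cost is lost precision and exposure to chance imbalance. With 50 per arm and an assumed 60% positivity, the standard error would fall by about 1.5% to 13% as phi rises from 0.2 to 0.5. Power would change from about 74/73/72% to 73/75/83%. These sizes depend wholly on assumed prevalence and correlation; if the correlation is low, there is little or nothing to gain. The missing table rows and the mismatch between 5.1.2 and 5.1.4 do not depend on those assumptions.

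**What to change.** For outcomes 16 and 18, prespecify:

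1. A risk difference from linear (identity-link) regression of five-month status on treatment, site and baseline status, as main effects. Use HC2 standard errors and a t reference on N minus the number of fitted parameters: N−4, or N−3 with site only. Report the 95% CI and P-value.
2. Adjustment for site only if fewer than 5 patients fall in one baseline category. This rule uses baseline data alone.
3. A rule for missing baseline status that also uses baseline data only, such as a missing-category indicator (one more parameter) or imputation of the overall mode, so that every FAS patient with an outcome stays in. Section 5.3.5 does not cover this case.
4. A statement that the residual-normality check and median-regression switch of 5.3.4 do not apply to these models; a 0/1 outcome would otherwise invite a switch that is of no use.
5. Newcombe and Fisher mid-P kept as the supportive unadjusted result.

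Also add baseline Berlin ≥ 2 and Stop-Bang ≥ 3 to the SAP 4.3 table, and reword 5.1.2 to agree with 5.1.4. Leave outcome 4 as it is.

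The cost is a short SAP paragraph, two table rows and a short program in Stata, which SAP 7 already names. No new data are needed, because the protocol flow chart has the questionnaires at screening. The downsides are an interval about 3–4% wider than Newcombe's at phi 0.2, and frequent loss of the baseline term at very high positivity. At 95% positivity, the chance that 4 or fewer of 100 patients are negative is about 43%. If the adjusted model is declined, the table rows and the rewording are still worth making.

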5.3.4 Assumption Checks and Alternative Analyses

The assumption of normally distributed residuals in linear regression will be checked by plotting histograms of the residuals and examining their descriptive statistics, such as mean, median, standard deviation, and coefficient of skewness.

In cases where the distribution of the residuals is deemed to deviate too much from the normal distribution to allow linear regression to be used, a median regression (i.e. a quantile regression) will be performed instead of the linear regression. Then, the difference in medians (with a 95% confidence interval and a P-value for equality of medians) will be reported instead of the difference in means.

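### For short, skewed integer scores, the median-regression fallback in SAP 5.3.4 can report a real shift as a median difference of exactly 0

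*SAP*

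**What the plan says.** SAP 5.3.2 sets the default: "All secondary continuous outcomes (see table in Section 5.1.4) will be analysed in the same manner as the primary outcome". That means linear regression on treatment, site and baseline. The table in SAP 5.1.4 types as continuous the AFSS frequency, duration, severity and global well-being outcomes (5, 6, 7, 10), the Berlin sum (15) and the Stop-Bang sum (17).

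SAP 5.3.4 then describes a residual check by histogram and summary statistics, including skewness. The switch is conditional: "In cases where the distribution of the residuals is deemed to deviate too much from the normal distribution to allow linear regression to be used". In that event "a median regression (i.e. a quantile regression) will be performed instead of the linear regression", and "the difference in medians (with a 95% confidence interval and a P-value for equality of medians) will be reported instead of the difference in means". No exception is made for scores with few values. Neither 5.3.4 nor the software section (7) names a standard-error method for the median regression.

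SAP 5.3.5 imputes missing outcomes as no change from baseline. SAP 2.4.1 classes all efficacy analyses other than the primary one as supportive or exploratory.

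**The concern.** Median regression suits a skewed but finely graded outcome. On a score with few values, the conditional median stays on one integer until enough patients cross it. If more than half of each arm sits at the lowest value, both medians equal that value, however the rest of the distribution moves. The usual standard error also needs a density at the median, and tied data do not have one.

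The trigger makes this worse. A pile-up at one end of a short scale produces skewed residuals, and skewed residuals prompt the switch. The difference in medians then replaces the difference in means, so no mean difference would be left to show the shift. AF symptom burden and symptoms of sleep apnea are stated secondary objectives (SAP 1.2.2). A real benefit on them could be published as no difference.

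**Working it through.** **The plan's own figure.** The fallback has no stated figure. The sample size in SAP 2.3 is reproduced to show that it is not involved.
- Target difference: 0.25 × 34 = 8.5 percentage points.
- Per group, n = 2(1.96 + 0.84)² × SD² / 8.5².
- SD 12: about 31.3, so 32, or 33 with the t distribution.
- SD 15: about 48.9, so 49, or 50 with t, which gives 100 in total.

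These match the SAP and concern AF burden only.

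**Inputs to the simulations.** From the SAP: 50 per arm (2.1), and treatment, site and baseline in the model (5.3.1, 5.3.2). Assumed: score ranges and shapes, and a baseline correlation of 0.5.

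**Set 1: 600 trials per row, no missing data.** Median regression was solved exactly. Its standard error used a fitted density at the median. The shift is on the underlying scale before rounding and truncation.

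| Assumed score | Shift | Median difference exactly 0 | Mean estimate, linear | Mean estimate, median | Power, linear | Power, median | Trials with absolute residual skewness above 1 |
|---|---|---|---|---|---|---|---|
| 0-3, floor-skewed | -0.5 | 100% | -0.19 | 0.00 | 0.320 | 0.002 | 99% |
| 1-10, floor-skewed | -1.5 | 98% | -0.53 | -0.01 | 0.307 | 0.008 | 100% |
| 1-10, long upper tail | -1.0 | 80% | -0.50 | -0.10 | 0.427 | 0.085 | 99% |
| 0-8, skewed | -0.8 | 1% | -0.79 | -0.88 | 0.983 | 0.982 | 82% |
| 0-3, symmetric | -0.4 | 32% | -0.38 | -0.34 | 0.832 | 0.638 | 0% |
| 0-4, symmetric | -0.6 | 8% | -0.55 | -0.61 | 0.820 | 0.608 | 0% |

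The Monte Carlo margin is about ±0.04 for a power near 0.5 (1.96 × √(0.25/600)) and ±0.02 for a rate near 0.05.

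The first three rows show the problem: a clear mean shift, a median difference of about 0, and residuals skewed enough to invite the switch. With 10% of outcomes imputed as no change, the share of exact zeros rose from 80% to 88% in row 3, from 1% to 5% in row 4, and from 32% to 57% in row 5.

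**Set 2: scores cut into four or nine levels, half-SD shift.**

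| Assumed score | Power, linear | Power, proportional odds | Power, median |
|---|---|---|---|
| Nine levels, floor-skewed | 54% | 59% | 6% |
| Four levels, floor-skewed | 56% | 61% | 2% |
| Four levels, top-heavy | 58% | 58% | 30% |
| Four levels, top-heavy, other cut-points | 66% | 68% | 48% |
| Four levels, symmetric | 75% | 77% | 55% |
| Nine levels, not skewed | 79% | 79% | 55% |

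The second and last three rows used 300 trials each. The first and third come from a separate run, in which the median difference was exactly 0 in 67-100% of trials on the skewed scores. In the 300-trial runs it was 0 in 97% for the floor-skewed four-level score, but in only 32% for the top-heavy one. The share therefore depends strongly on where the cut-points fall.

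**P-values.** When the standard error was computed from the residuals, it was exactly zero in 99% of the floor-skewed 0-3 trials and 61% of the floor-skewed 1-10 trials in Set 1, so no valid test exists there. Linear regression kept its false-positive rate at 0.037-0.067 across the short scores simulated, including the skewed ones.

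**The case against.** **Linear regression is the default, and the switch is a judgement.** This stands. On symmetric four-level scores, absolute residual skewness exceeded 0.5 in only 0-2% of trials, so the power loss there would seldom occur in practice. On skewed four-level scores it exceeded 0.5 in 87-99% of trials. The objection is therefore weakest where the harm is greatest.

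**A reader might infer that the fallback will declare null effects significant.** The documents do not support this. Simulated false-positive rates ran from 0.00 to 0.18, depending on score shape and on a standard-error method that the SAP does not name. The inflated rates arose mainly on symmetric scores, where the switch is unlikely. On skewed four-level scores the rates were 1-9%.

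**A reader might infer that the method fails on every short score.** It does not. The skewed 0-8 score in Set 1 lost nothing under a large shift, and its P-values were near nominal or conservative. On a symmetric 1-10 scale the P-values were adequate.

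**The score ranges are assumed.** This stands. Cut-offs of 2 for Berlin and 3 for Stop-Bang (SAP 5.1.2) are thresholds, not maxima. For AFSS, the documents name domains without levels.

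**Berlin and Stop-Bang have a second analysis.** Outcomes 16 and 18 dichotomise them, with Newcombe intervals and the Fisher mid-P test (SAP 5.3.3). This is a partial safeguard. The AFSS items have no such counterpart.

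**Proportional odds adds little power over linear regression.** This is true, with gains of 0 to 5 points in Set 2. It is a reason to keep the linear estimate as the reported result.

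**Conclusion.** The concern holds in a limited form. For a short integer score that is skewed, the only fallback in SAP 5.3.4 often returns a median difference of exactly 0 despite a real shift. Power then usually falls well below that of linear regression, to 2-6% against 54-56% on floor-skewed scores and by 18-28 points on top-heavy four-level scores. Ties make the accompanying P-values unreliable. Without skew the effect is smaller and the switch less likely.

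The size rests on assumed score ranges, shapes and baseline correlation. It should be read as what can happen, not as a forecast for a named outcome. Only supportive outcomes are touched. The primary outcome, the sample size and the main conclusion are unaffected, so this is a cheap improvement and not a threat to the trial.

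**What to change.** Add one paragraph to SAP 5.3.4, along these lines:

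> Integer scores with few possible values are exempt from the median-regression fallback. These are outcomes 15 and 17, and those of outcomes 5, 6, 7 and 10 whose scoring has few levels [list each with its range]. For them the linear-regression mean difference, with robust or bootstrap standard errors, remains the reported estimate. If the residuals are judged too non-normal, proportional-odds logistic regression with treatment, site and baseline is added as the supporting test, reported as a common odds ratio with 95% confidence interval. In sensitivity analysis 2 only the linear model is used, because mean-change imputation creates non-integer values.

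The list should be completed from the questionnaires' scoring rules before outcomes are examined by arm. The finely graded scores can keep the present rule, and outcomes 16 and 18 stay as they are.

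The cost is one paragraph and a standard model, with no new data and no change in sample size. The downside is that an odds ratio is less direct to interpret than a difference in score, which is why the mean difference stays as the reported estimate.
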